Randomized controlled trial comparing adult to pediatric colonoscope in obese patients.

NCT 06776913

Randomized controlled trial comparing adult to pediatric colonoscope in obese patients.

Corresponding author:

[name]

Email: [contact]

Address: [name]

Principal Investigator:

[name]

Email: [contact]

Address: [name]

Background

A colonoscopy is a routine procedure performed daily for various purposes, including colon cancer screening. Over time, colonoscopes have evolved and now come in different sizes, diameters, and flexibility levels. The choice of colonoscope typically depends on the endoscopist's preference, and anecdotal experience, with all types of instruments considered standard practice.

Several patient characteristics can make routine colonoscopy more challenging, such as diverticulosis and a history of previous surgeries, especially in the pelvic area. These challenging cases might influence the provider to choose one instrument over another, although there is a general lack of evidence demonstrating the superiority of specific colonoscopes in certain situations.

Obesity is one of the challenges encountered during routine colonoscopy. A retrospective study showed no difference in the performance of adult and pediatric scopes when matching the population's BMI. However, providers tend to choose adult scopes for higher BMI patients in unmatched populations. We designed this study to evaluate if adult and pediatric colonoscopes perform differently in obese patients, which both are considered standard practice in the study population.

Study objective.

The objective of this equivalence trial is to evaluate whether pediatric and adult colonoscopes achieve similar success rates in obese patients undergoing colonoscopy. Patients will be randomly assigned in a 1:1 ratio. The primary endpoint is the success rate of colonoscopy completion without switching instruments (defined in the main protocol).

Study hypothesis.

There is no significant difference between adult and pediatric colonoscopes in the evaluation of obese patients.

Study design.

Prospective randomized single-blinded Equivalence trial

- ➔ The patient is blinded regarding the instruments used.
- ➔ The endoscopist is not blinded. blinding is not feasible as the endoscopist would recognize the different instrument dimensions before the procedure.

Primary outcome

A composite of reaching the cecum, requiring less than 10 min for cecal intubation, without changing the scope type.

Secondary outcome

- ➔ cecal intubation rate (CIR)
- ➔ Terminal ileum intubation rate (TIIR): The provider will attempt terminal ileum in every patient for at least 2 minutes and up to 5 min.
- ➔ Insertion time (IT): time from insertion photo, to first cecal photo
- ➔ Ancillary maneuvers use (position change, pressure application, increase stiffness)
- ➔ Withdrawal time: time from terminal ileum picture or last cecal picture and rectal picture – 1 min per each intervention (polypectomy, cauterization...etc.)

Inclusion criteria

- BMI >30
- Screening and surveillance colonoscopy
- Male or female
- Age equal or more than 18 years

Exclusion criteria

- Colon surgery
- Therapeutic colonoscopy
- Inflammatory bowel disease
- Terminated procedure due to stool burden, stenosis, or obstructive mass.
- Colonoscopy for anemia
- History of incomplete colonoscopy due to technical difficulties

Randomization:

We will use the sealed envelope method for simple, stratified, randomization.

- Before the recruitment starts, we will prepare opaque sealed envelopes with a 1:1 ratio between the study groups, each envelope will have a serial number.
- On the day of the procedure, the endoscopist will be provided with a few envelopes (randomly selected serial numbers), he will choose one randomly and open it.
- All envelopes prepared before the recruitment process will be used during the study to ensure complete randomization and a 1:1 ratio between the study groups.
- The randomization will be stratified by providers performing the colonoscopy to ensure that each provider gets an equal assignment to both study groups to eliminate the bias that different providers' performances can introduce.

Study Operation:

1) Patient Invitation

- The research team will review the endoscopy schedule 1-2 weeks before the procedure date.

- All eligible candidates who meet the inclusion criteria will be invited to participate in the study.
- Candidates will be invited through A MyChart message or a mailed letter from the office of the provider performing the procedure.

2) Patient Consent

- The research coordinator will call the patient within 48 hours of sending the invitation. During this call, the study will be explained, and the consent process will be discussed (phone scripts attached). DocuSign will be used to send the consent form virtually. The patient will have 1-2 days to review the consent before a follow-up call is made.
- Patients who are interested in participating in the study, can elect to defer signing the paper consent to the day of the procedure.

Consent procedures for Patients at Coral Springs Family Health and Surgery Center

- For the patients who have not signed consent via DocuSign the endoscopist will obtain the signature for the consent prior to the procedure.
- Then the study coordinator will open the sealed envelope and communicate colonoscopy randomization to the provider.
- The endoscopist will return the signed consents to the study coordinator when they are in Weston.

3) Colonoscopy

- Endoscopists participating in the study will be informed in advance of the candidate's scheduled procedure date.
- Patients will receive the usual pre-procedure care before the endoscopy.
- The endoscopist will randomly select a sealed envelope to determine the patient group and assign the type of colonoscopy.
- As part of routine care, the endoscopist will capture photo documentation during the procedure, including insertion with time, cecum with time, terminal ileum with time, and end procedure with time.
- If the endoscopist is unable to intubate the terminal ileum, a second cecal photo will be taken before withdrawal.
- The endoscopist will document any additional maneuvers used, such as scope stiffening, changing patient position, applying pressure, or changing the scope.

- A brochure will be displayed near the computers used for procedure note documentation to remind providers of the required documentation elements after the procedure (attached).
- A research team member will retrospectively collect the study's primary and secondary outcomes from the endoscopy report and store them in REDCap.
- The patient's participation in the study will conclude at the end of the procedure.
- Trainees will not participate in the study procedures.

Electronic Consent Process

- An investigator or research coordinator will contact the invited candidates by phone one week before the scheduled procedure. The study's purpose, intervention, and consent process will be discussed during this call, which will be documented in the patient's chart.
- Patients interested in participating will receive the consent form through DocuSign, with instructions on how to complete it online.
- A follow-up phone call will be made 1-2 days later to answer any questions the patient may have.

Rationale for Electronic Consent (E-Consent)

- Many procedures are scheduled through open access, meaning the patient is scheduled by a provider other than the one performing the procedure, often from a different department. In these cases, the patient may not meet the performing physician until the day of the procedure.
- E-consent allows patients more time to consider participation without the pressure of deciding on the day of the procedure.

Sample size calculations

Assuming a 93% success rate in both arms and no true difference between colonoscope types, we aim to test statistical equivalence using a two-sided type I error of 0.05 and power of 80%. A 10% margin (± 0.10) in success rate is considered clinically acceptable and forms the basis for the equivalence hypothesis:

$$H_0: |p_1 - p_2| \geq 0.1$$

$$H_1: |p_1 - p_2| < 0.1$$

Based on these assumptions, a fixed sample size of 112 participants per group (total N = 224) is required. To preserve operating characteristics under the group sequential framework, the maximum sample size is inflated by an estimated factor of 1.082, yielding a maximum of 122 participants per group (total N = 244). The interim analysis will occur after enrollment of 122 participants (61 per group). (Group Sequential Methods with Applications to Clinical Trials by Jennison and Turnbull (pages 149–150) [2].

Study Variables

Date of birth, gender, race, BMI, previous pelvic\abdominal surgery, diverticulosis, colon prep (adequate- inadequate), type of colonoscopy, insertion time, cecum and terminal ileum intubation success, and procedure time. Please refer to the data collection sheet for details of the variables above.

Data Analysis

All statistical analyses will be conducted by a statistician from the Cleveland Clinic's Quantitative Health Sciences (CCF QHS) team, following the intention-to-treat (ITT) principle. This means that all randomized patients who receive one of the study interventions will be included in the primary analysis.

Baseline characteristics will be assessed for balance using standardized mean differences (SMDs), with a value less than 0.10 (absolute) indicating acceptable balance.

Missing data in baseline variables are expected to be minimal. If more than 5% of data are missing for any key variable, multiple imputation methods will be employed.

The primary outcome—successful completion of the colonoscopy (Yes/No)—will be analyzed as a binary endpoint. The effect of colonoscope type (adult vs. pediatric) will be evaluated using the Two One-Sided Tests (TOST) procedure, with a pre-specified equivalence margin of $\pm 10\%$. The absolute risk difference of 10% will also be translated into corresponding thresholds for odds ratios (OR = 2.72 or OR = 0.36) and relative risks (RR = 1.12 or RR = 0.893). Both unadjusted and adjusted logistic regression models, incorporating pre-specified covariates, will be used to estimate treatment

effects. Results will be presented as risk differences, relative risks, and odds ratios, with 95% confidence intervals derived via the g-computation method. Equivalence will be declared if the full confidence interval lies entirely within the specified equivalence range on each metric.

A per-protocol analysis will be conducted as a sensitivity analysis if there is substantial non-compliance. Additional sensitivity analyses will be considered to address missing data in outcome variables.

Secondary outcomes including cecal intubation rate (CIR), terminal ileum intubation rate (TIIR), insertion time (IT), use of ancillary maneuvers, withdrawal time, are considered independent of the primary outcome. Categorical secondary outcomes will be compared using chi-squared or Fisher's exact tests, while continuous variables will be analyzed using two-sample t-tests or Wilcoxon rank-sum tests as appropriate. Regression models adjusting for pre-specified covariates will also be considered.

Repeatedly measured outcomes will be analyzed using mixed-effects models, with study group and time point included as fixed effects, and subject ID as a random effect to account for within-subject correlation. This approach is robust to data that are missing at random (MAR) or missing completely at random (MCAR).

Data Security

Data, including patient information and consent, will be stored electronically in the Redcap system\DocuSign which is password-protected and on the secure Cleveland Clinic network. If physical paper sheets were used, the physical paper sheets' information would be transferred to Redcap and shredded on the day of data gathering.

Interim analysis

A group sequential design with a single interim analysis at 50% enrollment is proposed. This design allows early trial termination for either efficacy (equivalence) or futility (non-equivalence), while preserving the overall type I error ($\alpha = 0.05$) and power ($1 - \beta = 0.80$).

The design employs Hwang-Shih-DeCani gamma error spending functions [1]:

- Type I error: $\gamma = -4$ (O'Brien-Fleming-like)
- Type II error: $\gamma = 1$ (Pocock-like)

Analysis Stage	Type I Error Spending (Cumulative)	Type II Error Spending (Cumulative)
Interim (50%)	0.00596	0.124
Final (100%)	0.05	0.2

A non-binding futility boundary is used. Z-stopping-boundaries are shown below.

Analysis Stage	Equivalence		Non-equivalence	
	upper	lower	upper	lower
Interim (50%)	2.749966	-2.749966	1.152821	-1.152821
Final (100%)	1.959964	-1.959964	1.959964	-1.959964

Possible Harm to Subjects

Both study arms are considered standard treatment, and no anticipated harm is related to the study.

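### TIIR comes from an attempt of 2 to 5 minutes ended by an unblinded endoscopist and is compared without regard to attempt time, so unequal persistence by arm could create or hide a difference; a common-time supporting analysis is cheap.

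*Combined protocol and SAP*

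**What the plan says.** The Secondary outcome section lists TIIR and sets the attempt: "The provider will attempt terminal ileum in every patient for at least 2 minutes and up to 5 min". Nothing in the document says when, between those limits, an attempt that has not succeeded should end.

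Under Study design, "The endoscopist is not blinded. blinding is not feasible as the endoscopist would recognize the different instrument dimensions before the procedure".

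Under Randomization, "The randomization will be stratified by providers performing the colonoscopy to ensure that each provider gets an equal assignment to both study groups".

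Study Operation, 3) Colonoscopy, requires photos, "including insertion with time, cecum with time, terminal ileum with time, and end procedure with time", and adds: "If the endoscopist is unable to intubate the terminal ileum, a second cecal photo will be taken before withdrawal".

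Study Variables lists "insertion time, cecum and terminal ileum intubation success, and procedure time". It does not list the duration of the ileal attempt, but it refers to a data collection sheet that is not part of the document.

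In Data Analysis, "Categorical secondary outcomes will be compared using chi-squared or Fisher's exact tests". Covariate-adjusted regression for secondary outcomes is left as something to be considered. No analysis that uses attempt time is described.

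**The concern.** TIIR is a yes/no result, and the chance of a yes rises with the time spent trying. The permitted time varies 2.5-fold (5/2), and the person who decides when to stop knows the arm. An endoscopist who gives up at 2 minutes with one scope and persists to 5 with the other complies fully in both cases.

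The existing safeguards do not reach this:

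- Stratification by provider balances who performs the procedures. It does not make one provider try equally long with both scopes.
- Blinding the patient has no bearing on operator effort.
- A per-protocol analysis would keep both patients, since neither attempt departs from the protocol.
- Regression on baseline covariates does not adjust for attempt time.

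At stake is whether a TIIR difference, or the lack of one, can be put down to the instrument. The primary composite does not have this gap, because it scores cecal intubation against a fixed 10-minute limit.

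**Working it through.** **The plan's own figure.** The document gives no expected rate, margin or power for TIIR. The only figure borrowed here is the maximum of 122 per group (Sample size calculations). It reproduces: with 93% success in both arms, a margin of 0.10, one-sided 0.05 per test and z(1−β/2) for 80% power, n = 2 × 0.93 × 0.07 × (1.645 + 1.282)² / 0.10² = 111.5, so 112. Then 112 × 1.082 = 121.2, so 122.

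**Assumptions, none from the document.**

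- Both scopes have the same constant hazard of ileal intubation.
- Success by 2 minutes is p2 = 70%.
- TIIR is tested two-sided at 0.05 by uncorrected chi-squared with 122 per group. No alpha is stated for secondary outcomes.

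**Formula.** Success by limit t is p(t) = 1 − (1 − p2)^(t/2). With p2 = 0.70:

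- p(3) = 1 − 0.3^1.5 = 83.6%
- p(3.5) = 1 − 0.3^1.75 = 87.8%
- p(5) = 1 − 0.3^2.5 = 95.1%

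The probabilities below come from exact binomial enumeration.

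| Attempt limits, identical scopes | Rates | Spurious gap | P(p < 0.05) |
|---|---|---|---|
| 2 vs 2 min | 70.0% vs 70.0% | 0 | 5% |
| 3 vs 3.5 min | 83.6% vs 87.8% | 4.3 points | 16% |
| 2 min vs one quarter at 5, rest at 2 | 70.0% vs 76.3% | 6.3 points | 20% |
| 2 min vs one third at 5, rest at 2 | 70.0% vs 78.4% | 8.4 points | 32% |
| 2 vs 3 min, every patient | 70.0% vs 83.6% | 13.6 points | 72% |
| 2 vs 5 min, every patient | 70.0% vs 95.1% | 25.1 points | over 99% |

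The one-third row is 70.0 + 25.1/3 = 78.4.

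**Other 2-minute rates.** For 2 versus 5 minutes, p2 of 50%, 60%, 80% and 90% gives gaps of 32.3, 29.9, 18.2 and 9.7 points.

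**Some patients never intubable.** If a share c can never be intubated, p(t) = (1 − c) × [1 − (1 − p2/(1 − c))^(t/2)]. With c = 10% and p2 = 70%:

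- 3 vs 3.5 min: 3.0 points, 9.5% of trials significant
- 2 vs 3 min: 10.6 points, 49%
- 2 vs 5 min: 17.9 points, 94%

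**Hiding a real difference.** Let one scope have 0.4 times the hazard of the other. At 2 minutes its rate is 1 − 0.3^0.4 = 38.2% against 70.0%, a gap detected in over 99% of trials at equal effort. If the worse scope is tried for 5 minutes and the better for 2, the worse reaches 1 − 0.3^(0.4 × 2.5) = 70.0%. The rates are then equal, and the chance of a significant result is 5%.

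**Common time point.** Scored at 2 minutes, identical scopes give 70% in both arms whatever limit each attempt had, because every unsuccessful attempt lasts at least that long. This holds so far as the first cecal photo marks the start of the attempt.

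**The case against.** The strongest reply is that the window already standardizes the attempt: every patient gets a minimum and there is a cap. TIIR within a bounded, operator-judged attempt is a legitimate pragmatic outcome. If an endoscopist stops sooner because a scope handles poorly at the valve, that is partly an effect of the scope. Nothing in the document shows that effort will differ by arm; the Background's remarks on preference concern choosing a scope, not persistence at the ileum. The unseen data collection sheet may record attempt time.

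Much of this stands, and it limits what can be claimed. A reader might infer that the TIIR comparison cannot be answered as written. The document does not support that: bias needs unequal effort, and with equal effort the test holds its level. A reader might also take the 72% for 2 versus 3 minutes as a mild case. It is a boundary case, since one arm must stop every failed attempt at the 2-minute floor and every patient in the other must have a limit of exactly 3. The same average limit of 3 minutes, made up of one third at 5 and two thirds at 2, gives 32%.

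What the reply does not remove is that the planned analysis cannot tell whether effort was equal. Even if the sheet records attempt time, no described analysis uses it.

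**Conclusion.** The point holds in a conditional form. An open window, an unblinded operator and a raw comparison of rates leave TIIR exposed to differential persistence by arm. Such persistence could produce a difference between equivalent scopes or conceal a real one.

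Under the assumed 70% rate and constant hazard, the spurious gap runs from about 4 points for a half-minute imbalance to 25 points at the extreme, and it is smaller if some patients can never be intubated. These sizes rest wholly on assumed rates and attempt times. They show what the rule permits, not what will happen.

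The issue concerns one of five secondary outcomes. The primary composite, sample size and interim boundaries are untouched. It is a worthwhile, inexpensive improvement rather than a flaw in the trial's main question.

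**What to change.** Leave the attempt and the TIIR definition as they are, and add three things to Data Analysis before outcome data are examined:

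1. Derive the time from the first cecal photo to the terminal ileum photo or, after failure, to the second cecal photo. Report it by arm.
2. Prespecify a supporting comparison of TIIR at a common time: an ileal photo within 2 minutes of the first cecal photo, matching the protocol's minimum attempt. Present it beside the overall rate.
3. State that a TIIR difference will be attributed to the scope only if the two analyses agree.

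The cost is one derived variable and a few lines of text. The photo list asks for a time on the cecal image; it is worth confirming that the second cecal photo is also timed.

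There are real limits. The first cecal photo is an imperfect proxy for the start of the attempt, and the operator influences the interval between them. Some compliant successes will therefore count as late, which is why the 2-minute figure should support TIIR and not replace it. A time-to-intubation analysis censored at the end of the attempt is possible, but the operator chooses the censoring time and it may be informative, so it should be exploratory only.

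### Withdrawal time starts in the ileum if the ileum was entered and in the cecum if it was not, so a secondary outcome partly carries another compared outcome; the likely effect is seconds and the remedy is one photo

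*Combined protocol and SAP*

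**What the plan says.** The Secondary outcome section defines the measure as "Withdrawal time: time from terminal ileum picture or last cecal picture and rectal picture", with one minute taken off for each intervention. It gives no rule for choosing between the two starting photos.

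The Colonoscopy part of Study Operation supplies that rule indirectly: "If the endoscopist is unable to intubate the terminal ileum, a second cecal photo will be taken before withdrawal". The timed photos it lists for routine capture are introduced as "including insertion with time, cecum with time, terminal ileum with time, and end procedure with time". No cecal photo after ileal entry is requested.

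Ileal intubation is tried in everyone: "The provider will attempt terminal ileum in every patient for at least 2 minutes and up to 5 min". The resulting rate and withdrawal time stand side by side in Data Analysis: "Secondary outcomes including cecal intubation rate (CIR), terminal ileum intubation rate (TIIR), insertion time (IT), use of ancillary maneuvers, withdrawal time". For measures such as withdrawal time, "continuous variables will be analyzed using two-sample t-tests or Wilcoxon rank-sum tests as appropriate". Covariate-adjusted regression is only to be considered, and nothing there refers to whether the ileum was entered.

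**The concern.** Whether the ileum is entered is known only after randomization, could depend on the instrument, and is itself compared between arms. If it also decides where the withdrawal clock starts, the two arms may be timed over different mixtures of intervals.

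After success, the interval contains whatever ileal inspection follows the photo, the return to the cecum, and the colonic withdrawal. After failure, it contains the colonic withdrawal alone. If one colonoscope entered the ileum more often, its mean withdrawal time would be longer even with identical colonic withdrawal. A reader who saw a higher TIIR and a longer withdrawal in the same arm could not tell an instrument effect from an effect of the definition. Because the error is systematic, a larger sample would not remove it.

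**Working it through.** **Which interval is timed.**

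| | Ileum entered | Ileum not entered |
|---|---|---|
| Start photo | Terminal ileum | Second cecal, before withdrawal |
| Ileal attempt (2 to 5 min) | Excluded | Excluded |
| Ileal time after the photo, and return to cecum | Included | Not present |
| Colonic withdrawal | Included | Included |

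Only the third row differs.

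**Formula.** Let p be the proportion with ileal entry among patients who have a withdrawal time, and t the mean time from ileum photo back to cecum. With equal colonic withdrawal in arms A and B:

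artefact in the mean difference = p_A × t_A − p_B × t_B

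If t is the same in both arms, this becomes (p_A − p_B) × t. If p is also the same, it is zero.

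**Inputs.** The documents give no TIIR, no ileal time, no standard deviation (SD) for withdrawal time and no expected withdrawal time, so there is no figure of the plan's own to reproduce on this point. Assumed ranges:

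- TIIR difference: 0 to 20 percentage points
- t: 15 to 120 seconds, equal in both arms
- SD of withdrawal time: 2, 3 or 4 minutes

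The one input from the plan is the group size, used only for scale. Sample size calculations states that "a fixed sample size of 112 participants per group (total N = 224) is required" and inflates it by 1.082: 112 × 1.082 = 121.2, rounded up to 122, which agrees with "yielding a maximum of 122 participants per group (total N = 244".

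**Standard error (SE) of the mean difference.** SE = SD × √(2/122) = SD × 0.128:

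- SD 2 min: 120 s × 0.128 = 15.4 s
- SD 3 min: 180 s × 0.128 = 23.0 s
- SD 4 min: 240 s × 0.128 = 30.7 s

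**Results.** With b the artefact, the chance that a nominal two-sided 5% test rejects when colonic withdrawal does not differ is 1 − Φ(1.96 − b/SE) + Φ(−1.96 − b/SE), by normal approximation.

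| TIIR difference | t | b | SD 2 min | SD 3 min | SD 4 min |
|---|---|---|---|---|---|
| 0 points | any | 0 s | 5.0% | 5.0% | 5.0% |
| 5 points | 15 s | 0.05 × 15 = 0.75 s | 5.0% | 5.0% | 5.0% |
| 10 points | 30 s | 0.10 × 30 = 3 s | 5.4% | 5.2% | 5.1% |
| 10 points | 60 s | 0.10 × 60 = 6 s | 6.8% | 5.8% | 5.4% |
| 20 points | 60 s | 0.20 × 60 = 12 s | 12.2% | 8.2% | 6.8% |
| 20 points | 120 s | 0.20 × 120 = 24 s | 34.6% | 18.0% | 12.2% |

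The SE assumes that all 122 patients per group contribute. Fewer would raise the SE and bring the rejection rates closer to 5%.

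**The case against.** **The plan already deals with the larger distortion.** By using the last cecal photo, and by asking for a second one after a failed attempt, it keeps the 2 to 5 minute attempt out of the interval on both paths. This stands. A reader might infer that the attempt itself lengthens withdrawal time in one group of patients; the text does not support that.

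**The bias is conditional.** The study hypothesis is that the instruments do not differ. With equal TIIR and equal ileal time there is no artefact, and nothing in the documents shows that either will differ. This stands too. It would be wrong to say that one arm will have longer withdrawal times because of the definition.

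**A common start already exists.** The first cecal photo is timed in every patient whose cecum is reached, and ileal success is a recorded variable, so results could also be shown by ileal status. This stands in part. It is not true that no common start is available. But the interval from the first cecal photo includes the ileal attempt, and splitting by ileal success conditions on a post-randomization result. Either would serve as a sensitivity analysis. Neither isolates colonic withdrawal for a randomized comparison.

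**The end photo.** The definition ends at a rectal picture, whereas the capture list names an end-of-procedure photo. A reader might infer that the end point is not captured. The list is introduced as inclusive, the two may be the same photo, and the data collection sheet and brochure to which the protocol refers are not among the documents reviewed. This is no more than a naming difference.

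**Conclusion.** The point holds as a matter of definition. Taken together, the two sections make the start of withdrawal time depend on ileal intubation success, a compared post-randomization outcome, and the analysis plan does not address this. Choosing the start photo by ileal success is the natural reading of the two sections, although the definition itself does not state it.

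The expected size is small. On assumed values it is 3 to 6 seconds for a 10-point TIIR difference and 30 to 60 seconds of ileal time, against an SE of 15 to 31 seconds, and a nominal 5% test would then reject in about 5.1% to 6.8% of trials. It reaches 24 seconds, with rejection in about 12% to 35% of trials, only if a 20-point difference and 120 seconds occur together. All of this assumes the same ileal time in both arms.

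One secondary outcome is affected. Nothing here supports a doubt about the primary composite, the equivalence margin or the sample size. It is worth correcting because the dependence is systematic and cheap to remove, not because it threatens the trial's conclusion.

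**What to change.** 1. In Study Operation, Colonoscopy, require a timed cecal photo immediately before colonic withdrawal in every patient whose cecum is reached, whether or not the ileum was entered. This extends to ileal successes a photo already requested after failed attempts.
2. In Secondary outcome, define withdrawal time as starting at that photo for all patients, and drop the alternative start at the ileum photo. The per-intervention deduction need not change for this purpose.
3. Use one name for the end photo in both sections. This is a clarification of wording only.

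The cost is one extra photo in patients with a successful ileal intubation, edits to two sections, and an updated reminder brochure. No analysis method or sample size changes. If patients have been enrolled before the change, those with ileal success will lack the new start photo; report their number and show the interval from the first cecal photo as a sensitivity analysis, noting that it includes the ileal attempt.

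### The 112 per group rests on 0.05 in each one-sided test, but equivalence is judged with 95% confidence intervals; risk-difference power at the maximum of 122 per group is about 72–73%, not 80%

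*Combined protocol and SAP*

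**What the plan says.** **Sample size calculations.** The premise is "Assuming a 93% success rate in both arms and no true difference between colonoscope types". The error rates are given as "two-sided type I error of 0.05 and power of 80" per cent. On the margin: "A 10% margin (± 0.10) in success rate is considered clinically acceptable". The result is stated as "Based on these assumptions, a fixed sample size of 112 participants per group (total N = 224) is required". This is inflated by 1.082 for the sequential design to a maximum of 122 per group (244 in total), with an interim look at 61 per group.

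**Data Analysis.** The primary comparison uses the two one-sided tests (TOST) procedure with a ±10% margin. Risk differences, relative risks and odds ratios are to be reported "with 95% confidence intervals derived via the g-computation method". Equivalence is declared only if the whole interval lies inside the range on each of these metrics.

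**Interim analysis.** The design is said to preserve an overall type I error of 0.05 and power of 0.80. Cumulative type I error spending is 0.00596 at the interim and 0.05 at the end. The equivalence boundaries are ±2.749966 and ±1.959964. The interim non-equivalence boundary is ±1.152821, and futility is non-binding.

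No section mentions a 90% interval or an alpha of 0.05 for each one-sided test.

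**The concern.** In TOST, testing each side at level alpha is the same as asking whether the 1 − 2·alpha interval lies inside the margin. An alpha of 0.05 per test pairs with a 90% interval and a critical value of 1.645. A 95% interval pairs with 0.025 per test and 1.960. The phrase in the sample size section, "using a two-sided type I error of 0.05 and power of 80" per cent, does not say which is meant. The number of patients appears to follow the first convention, while the interval level and the boundary table follow the second.

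If so, the power stated for the trial is not the power of the rule that will decide it, and the chance that truly equivalent scopes give an inconclusive result is higher than planned. The verdict is also left open when the 90% interval lies within ±10 points and the 95% interval does not: the TOST wording and the interval wording could then be read to opposite conclusions.

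**Working it through.** **Inputs.** p = 0.93 in both arms, true difference 0, margin 0.10, power 0.80, 1:1 allocation, 112 per group fixed and 122 maximum (study objective and Sample size calculations); 95% intervals (Data Analysis); boundaries 2.749966 and 1.959964 (Interim analysis).

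**1. Reproducing 112.** With a true difference of zero, the type II error is split over the two tests:

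n = 2p(1−p)·(z₁₋α + z₁₋β/₂)² / margin², with 2p(1−p) = 0.1302 and z₀.₉₀ = 1.282.

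- α = 0.05 per test: 0.1302 × (1.645 + 1.282)² / 0.01 = 111.5, so **112**. Then 112 × 1.082 = 121.2, so 122. Both of the plan's figures are reproduced.
- α = 0.025 per test: 0.1302 × (1.960 + 1.282)² / 0.01 = 136.8, so **137**.

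Other variants do not return 112. Using z₀.₈₀ gives 81 (α = 0.05) or 103 (α = 0.025). Continuity-corrected forms give 99.5, 121.4, 130.7 and 156.2. Superiority of 93% over 83% gives 130 (one-sided), 165 (two-sided) or 185 (continuity-corrected).

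**2. Which alpha the boundaries use.** The spending function with γ = −4 gives 0.00596 at half the information, as tabled. z(1 − 0.00596/2) = 2.749966 is the tabled interim value; z(1 − 0.00596) would be 2.514. The final value, 1.959964, is z(1 − 0.05/2). Both values therefore match a halved alpha.

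**3. Power on the risk difference, no futility stop.** Power = 2Φ(0.10/SE − c) − 1, with SE = √(0.1302/n). Exact figures enumerate the binomial outcomes with Wald intervals.

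| n per group | SE | 0.10/SE | 90% interval, c = 1.645 | 95% interval, c = 1.960 |
|---|---|---|---|---|
| 112 | 0.0341 | 2.933 | 80.2% (exact 80.3%) | 66.9% (exact 68.0%) |
| 122 | 0.0327 | 3.061 | 84.3% (exact 84.0%) | 72.9% (exact 72.1%) |

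Simulating the two-stage design with the tabled equivalence boundaries at 61 and 122 per group also gives 72.9%. The interim look adds nothing here: at 61 per group 0.10/SE is 2.16, below 2.75, so equivalence cannot be declared at that look under the planning assumptions.

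**4. Type I error.** The chance of crossing 2.750 at the interim or 1.960 at the end on one side is 0.026. Requiring both one-sided tests to pass, simulation at a true difference of 0.10 gives about 0.025. Both are below the stated 0.05.

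**5. Boundaries on 0.05 per side.** Spending 0.05 on each side with γ = −4 gives 2.514 at the interim and 1.664 at the end. The latter corresponds to 2Φ(1.664) − 1 = 90.4%. Simulated risk-difference power at 122 per group is then 83.8% without futility stopping.

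**6. Limits of these figures.** If ±1.152821 is read as a bound on each one-sided statistic and is followed, power at 122 per group is about 57% with the tabled equivalence boundaries and about 63% with 2.514 and 1.664. If the relative-risk and odds-ratio ranges must be met as well, unadjusted Wald intervals give about 9% at 95% and about 26–28% at 90% (c = 1.664 and 1.645), without futility stopping.

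**The case against.** **The error is on the safe side.** This stands. A 95% interval makes a false claim of equivalence less likely than the plan allows, and both scopes are standard practice in this population. A reader might infer from an alpha mismatch that type I error is inflated; step 4 shows the reverse. What fails is the power statement.

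**112 is only an intermediate figure.** This also stands. A reader might take the 67% at 112 per group and conclude that equivalent scopes would be missed far more often than planned. The documents set the maximum at 122 per group, where the miss rate is about 27–28% against a planned 20%. That is a shortfall of 7 to 8 points, not 13.

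**The Interim analysis section does not define its Z statistic.** This is fair. That the interim value equals z(1 − 0.00596/2) shows a halved alpha, but reading the table as one-sided TOST statistics is an assumption. The firm evidence is the 95% interval rule in Data Analysis.

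**The sample size section says two-sided 0.05, so 1.960 was intended all along.** Then 112 is the figure that is wrong, because that reading needs 137. On either reading one stated number has to change.

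**The alpha mismatch is not the main loss of power under the rule as written.** This is right if equivalence is required on the odds ratio too (step 6). That is a separate matter and cannot restore the missing power. It does mean that correcting alpha alone does not secure 80% for the full written rule, and a reader should not infer that it does.

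**Conclusion.** The point holds. The sample size uses 0.05 per one-sided test, whereas the interval level and the boundary values correspond to 0.025. On the risk difference alone, power is about 72–73% at 122 per group (67–68% at 112), not the 80% claimed.

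This rests on 93% success in both arms, no true difference, Wald-type intervals and no futility stop. The plan's g-computation intervals could differ somewhat. Following the futility bound, or requiring equivalence on the odds ratio as well, lowers power further. The size of the first effect depends on what the undefined Z statistic is, and that of the second on the interval method. The documents support neither a claim of inflated type I error nor a claim that one change of alpha repairs the whole decision rule.

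**What to change.** Before any comparison of outcomes by arm, put the sample size, interval level and boundaries on one alpha, and name the risk difference as the metric that decides equivalence and to which the stated power refers. Two routes keep the planned 122 per group:

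- **(a) 0.05 per one-sided test.** State TOST at 0.05 for each test and replace the 95% decision interval with the matching 90% interval (about 90.4% at the final look). Define the Z statistic and recompute the whole boundary table. If the tabled values are one-sided TOST statistics, the equivalence bounds become 2.514 and 1.664; the futility bounds must be re-derived too. This route matches the calculation that gave 112, but it loosens the written success criterion, so it must be settled before results are seen.
- **(b) 0.025 per one-sided test.** Keep the 95% interval and the halved alpha, and restate power as about 72% at 122 per group for the risk difference. Add that it is lower if the futility bound is followed or if equivalence is also required on the odds ratio.

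The cost is revised wording in three sections plus, under (a), a recomputed boundary table or, under (b), a less favourable stated power. Keeping both the 95% interval and 80% power would instead need 137 per group in a fixed design. With the plan's own factor that is 137 × 1.082 = 148.2, so about 149 per group, provided the factor is re-derived and still applies.
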